6.1.1. Dosing Regimen

6.1.1.1. Dosing Regimen in Stage 1

Stage 1 includes up to 3 consecutive cohorts, with 24 participants in each cohort. Participants from 1 cohort will not be allowed to enroll into the subsequent cohort(s). Participants in each cohort will be randomized into 1 of 4 intervention arms:

- AGN-242428 (N = 9)
- AGN-231868 (N = 9)
- AGN-242428 vehicle (N = 3)
- AGN-231868 vehicle (N = 3)

The morning dose of the assigned study intervention will be administered by the site staff at Visits 2, 3, 4, and 5 (except for Early Termination visit).

All participants will receive 1 drop of the assigned intervention to the left eye on Day 1 (Visit 2) (administered by the site staff). On Days 2 to 14, the participants will administer a single drop to both eyes, twice daily (approximately 12 hours apart). On Day 15 (Visit 5), the participants will be administered a single dose to both eyes.

6.1.1.2. Dosing Regimen in Stage 2

In Stage 2,

approximately 250 participants, who requalify at Baseline visit, will be randomized into 5 groups, in a 1:1:1:1:1 ratio within each site, as follows:

- AGN-242428 (N = 50)
- AGN-242428 vehicle (N = 50)
- AGN-231868 (N = 50)
- AGN-231868 vehicle (N = 50)
- Xiidra (N = 50)

The morning dose of the assigned study intervention will be administered by the unmasked site staff at Visits 2, 3, 4, 5, and 6. Any masked staff members should not be present in the room during dosing to prevent unmasking.

During the intervention period, participants will be instructed to administer 1 drop of assigned intervention twice daily (approximately 12 hours apart) to both eyes on Days 1 to 41. On Day 42, the participants will be administered a single dose to both eyes. The highest tolerated doses of AGN-242428 and AGN-231868 (established in Stage 1) will be selected for testing in Stage 2 to maximize the potential to achieve proof of concept.

6.2. Preparation/Handling/Storage/Accountability

The investigator or designee must confirm appropriate temperature conditions have been maintained during transit for all study intervention received and any discrepancies are reported and resolved before use of the study intervention.

Only participants enrolled in the study may receive study intervention, and only authorized site staff may supply or administer study intervention. All study intervention must be stored in a secure, environmentally controlled, and monitored (manual or automated) area with access limited to the investigator and authorized site staff.

The investigator, designee, institution, or the head of the medical institution (where applicable) is responsible for study intervention accountability, reconciliation, and record maintenance (ie, receipt, reconciliation, and final disposition records).

[figure not shown]
All used and unused study intervention must be returned to the sponsor at the end of the study. Reconciliation will be performed when the study intervention is returned, and all study intervention must be accounted for.

Further guidance and information for the final disposition of unused study interventions are provided in the Study Procedure Manual.

[figure not shown]
6.3. Measures to Minimize Bias: Randomization and Masking

6.3.1. Method of Intervention Assignment

All participants will be centrally assigned to randomized study intervention using an IWRS. Before the study is initiated, the log-in information and directions for the IWRS will be provided to each site.

Stage 2:

[figure not shown]
250 participants, who requalify at the Baseline visit (Day 1 [Visit 3]), will be randomized in a 1:1:1:1:1 ratio, within each site, to receive AGN-242428, AGN-242428 vehicle, AGN-231868, AGN-231868 vehicle, or Xiidra.

The IWRS system will provide the site with the specific kit numbers for each randomized participant at the time of randomization. Sites will dispense the study intervention according to the IWRS instructions and the SoA (Section 1.3). Returned study intervention must not be redispensed to the participants. All IWRS notifications are to be maintained with the study source documents.

[figure not shown]
The IWRS will be programmed with mask-breaking instructions. In case of an emergency, the investigator has the sole responsibility for determining if unmasking of a participant's intervention assignment is warranted. Participant safety must always be the first consideration in making such a determination. If the investigator decides that unmasking is warranted, the investigator should make every effort to contact the sponsor prior to unmasking a participant's intervention assignment unless this could delay emergency treatment of the participant. If a participant's intervention assignment is unmasked, the sponsor must be notified within 24 hours after breaking the mask. The date and reason that the mask was broken must be recorded in the source documentation and case report form, as applicable.

6.3.2. Masking

In Stage 1, the investigator, site staff (with the exception of unmasked pharmacy staff), and participants will be fully masked to study intervention and all interventions will be provided in identical single-use bottles and cartons.

In addition, further steps will be taken in Stage 2 to reduce the concern that exists in dry eye clinical trials, in which the active study intervention elicits a significant participant response (for example, ocular irritation, dysgeusia, and reduced visual acuity are reported in 5% to 25% of patients administered Xiidra [Xiidra US package insert 2016]), and where the documentation and subsequent follow-up of these reports may imply that the affected participants are on the active study intervention and create bias in the completion of the trial's efficacy assessments. To reduce the potential for bias in participant-reported symptoms and investigator-graded signs, certain parties will not be made aware of changes in a participant's medical status, concomitant

medications, or AEs until their role in completing the efficacy-related assessments conducted on any given day is complete. The parties subject to this restriction include any individual who will participate in an assessment related to trial efficacy (eg, an investigator grading staining, technicians explaining and recording questionnaires, or a technician facilitating CAE exposure). The unmasked staff members who administer the intervention in the morning of visit days will also not be allowed to participate in any efficacy or safety-related assessments conducted on any given day, considering that Xiidra vials will look different than vials with AGN-242428, AGN-231868, and their vehicles, which can imply that the participant is on the active study intervention. This information restriction is to be suspended when deemed medically necessary by the investigator, in the event of a medical emergency, or in order to protect the rights and welfare of a participant.

Participant-Reported Information: For each day on which there is a participant visit, an appropriately trained and delegated technician will be designated as the "Non-Efficacy Technician". Multiple technicians may receive this designation, as needed, and it will not affect their participation in the clinical trial beyond the day on which the assignment is made. This technician is primarily responsible for conducting medical status updates with the participant at the beginning of the visit. As part of the update, the technician will query any changes to the participant's health and concomitant medications, record new participant-reported AEs, and follow-up on any existing AEs or other problems. The technician will request that the participant avoid discussing their medical status, AEs, and experience with the investigational product with other technicians, participants, or the investigator unless specifically told otherwise by clinical trial staff or in the event of a medical emergency. The designated Non-Efficacy Technician may assist with or perform other tasks that have no bearing on trial efficacy and for which they are appropriately trained and delegated (eg, pregnancy tests, participant check-in, participant check-out, etc.).

Investigator-Graded Signs: The investigator grading participant signs will not be made aware of a participant's new AEs, updates to existing AEs or problems, or changes in medical status and concomitant medications until after all efficacy assessments in which they will participate are complete at any given visit. For visits at which the participant will enter the CAE, the investigator's role in the efficacy assessments will not be complete until after the post-CAE evaluation at a minimum. When the investigator is no longer involved with the completion of a participant's efficacy assessments for a given visit, they are to evaluate and grade AEs and address other issues as needed with the participant.

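### The Stage 2 safeguard that keeps adverse event information from efficacy assessors works by day or visit, not by participant, so staff who learned a participant's events earlier may assess that participant's efficacy later

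*Protocol*

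**What the plan says.** Protocol Section 6.3.2 (Masking) adds safeguards for Stage 2 because reactions to an active drop, and the recording and follow-up of those reactions, may point to the arm and bias efficacy assessments. Its example is Xiidra: eye irritation, altered taste and reduced acuity, at 5% to 25%. The rules are:

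- **All efficacy assessors** (sign graders, technicians handling questionnaires, staff running the controlled adverse environment, CAE) are kept from AE, medication and health-status news "until their role in completing the efficacy-related assessments conducted on any given day is complete".
- **The Non-Efficacy Technician** takes the status update when the visit begins. The tasks are to "record new participant-reported AEs, and follow-up on any existing AEs or other problems". Of the designation, the section says "it will not affect their participation in the clinical trial beyond the day on which the assignment is made".
- **The grading investigator** is shielded "until after all efficacy assessments in which they will participate are complete at any given visit". After that, "they are to evaluate and grade AEs and address other issues as needed with the participant".
- **Unmasked dosing staff** "will also not be allowed to participate in any efficacy or safety-related assessments conducted on any given day", the reason being "considering that Xiidra vials will look different than vials with AGN-242428, AGN-231868, and their vehicles".

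The information restriction may be lifted for medical necessity, an emergency, or a participant's rights and welfare. Section 6.1.1.2 treats unmasked dosing staff and masked staff as separate groups and keeps the latter out of the room at dosing. Section 4.1 places exploratory efficacy at Days 14 and 28 without the CAE and at Day 42 with and without it.

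**The concern.** The hazard named in Section 6.3.2 is knowledge that a member of staff carries about a participant. The remedy controls only when news arrives during a visit. It stops an assessor hearing today's AE before today's assessment, but it does not stop a person who heard that participant's AE two weeks ago from assessing the same participant today. Efficacy is measured on the same people at three post-baseline visits, so the gap recurs by design.

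At stake are symptom recording, CAE conduct and sign grading at Days 28 and 42. Day 42 is the only post-baseline visit with efficacy under the CAE. These endpoints are exploratory, but Sections 4.2.3 and 4.2.4 describe Stage 2 as seeking proof of concept, and Section 2.1 says the data will guide development.

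**Working it through.** There is no design figure to reproduce. Section 9.2 says the sample size has no statistical basis, and Section 6.3.2 makes no numerical claim about masking. The check is a reading of the rules by role, followed by an illustration of scale.

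**1. How long each restriction lasts**

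| Role | What the person learns | Stated duration | Barred from the same participant's later efficacy assessments? |
|---|---|---|---|
| Non-Efficacy Technician | New and continuing AEs | Day of assignment, expressly | No |
| Other efficacy assessors | AE news once their role is done | That day | No |
| Grading investigator | AEs, which this person must then grade | That visit | No |
| Unmasked dosing staff | Vial appearance | Unclear | Not stated either way |

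**2. Chronology.** The technician's update comes at the start of the visit, so the first update that can hold AEs from the weeks after the first randomised dose is at Day 14. Information taken then can reach the Day 28 and Day 42 assessments; information taken at Day 28 can reach Day 42. Nothing in the supplied text closes either path.

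**3. The investigator.** This path needs no assumption about technician rotas. If one investigator grades successive visits, the protocol itself has that person review the AEs between gradings. Table 8-8 prefers the same grader for anterior chamber cells and flare. That is a slit-lamp safety measure, but it shows that continuity of grader is expected.

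**4. Scale of arm-suggestive reactions.** Inputs: 50 participants per arm (Section 6.1.1.2) and 5% to 25% (Section 6.3.2).

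- Expected Xiidra participants with a given reaction: 50 × 0.05 = 2.5, to 50 × 0.25 = 12.5.
- Chance of at least one in the arm: 1 − (1 − p)^50, which is 0.923 at 5% and about 1.000 at 25%.

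**5. How informative one reaction is.** With equal allocation to five arms the prior for Xiidra is 0.20. If r1 is the Xiidra rate and r0 the common rate in the other four arms,

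P(Xiidra | reaction) = 0.2·r1 / (0.2·r1 + 0.8·r0).

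The documents do not give r0. Values of 1% and 5% are assumed for illustration.

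| r1 | r0 (assumed) | P(Xiidra given reaction) |
|---|---|---|
| 5% | 5% | 0.200 |
| 5% | 1% | 0.556 |
| 25% | 5% | 0.556 |
| 25% | 1% | 0.862 |

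A reaction may thus carry no information (0.200, equal to the prior) or be strongly suggestive (0.862). The documents do not say where the trial lies in that range.

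**6. Vials.** Protocol Section 6.1 and Stage 2 SAP Section 2.3 say that both AGN products and their vehicles come in identical vials. A vial therefore shows Xiidra or not Xiidra, and cannot separate an AGN product from its vehicle.

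**The case against.** The strongest reply concerns the dosing staff. A reader might infer that their ban lapses each evening, because the phrase about any given day sets a same-day limit earlier in the same paragraph. The text does not support stating this as fact. The phrase can equally mean every day. Section 6.1.1.2 keeps masked and unmasked staff apart, the stated reason (different vials) does not expire overnight, and where the protocol wanted a limit to lapse it said so, for the technician only. What remains is an unstated duration that should be clarified.

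A reader might also infer that the AGN-versus-vehicle comparisons are compromised. Vials cannot do this. AE knowledge could do so only if an AGN drop had a recognisable effect, and Sections 2.2.1.4 and 2.2.2.4 report no ocular clinical experience with either compound.

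Third, one could assume that technicians are rostered at random from a pool of k and compute the chance that the Day 42 efficacy technician took that participant's update at Day 14 or 28: 1 − ((k−1)/k)², or 44%, 31% and 23% for k = 4, 6 and 8. The arithmetic is right, but no section gives k, a shared pool or random rostering. The figure also counts any update, not one containing a revealing reaction, so it is not an estimate of unmasking.

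Finally, efficacy is exploratory, Section 9.1 plans no hypothesis tests, and parts of the efficacy text are redacted and the Study Procedure Manual is not supplied. That lowers the stakes and leaves room for unseen detail. It does not remove the point: a stricter rule elsewhere would conflict with the express clause on the technician.

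**Conclusion.** The concern holds for AE information. By its own terms the safeguard ends with the day or visit, and the person who records the AEs is expressly free afterwards to take part in the same participant's later efficacy assessments. For dosing staff the finding is only that the duration of the ban is not stated, with consequences confined to comparisons with Xiidra.

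No size of bias can be derived. The documents support 2.5 to 12.5 of 50 Xiidra participants with a given reaction, and nothing on the rate in the other arms. A reader might go on to infer that assessors will usually know the arm by Day 42. A rate of 5% to 25% per reaction does not show that, and a reaction is not in itself an unmasking.

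The conclusion assumes that staff at a site can hold different roles for the same participant at different visits, which the protocol permits, and that no unseen text overrides Section 6.3.2. It warrants a change in wording. It does not undermine the primary safety and tolerability objective.

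**What to change.** In Section 6.3.2:

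1. Replace the one-day clause with a participant-specific rule for all of Stage 2. Anyone who has acted as Non-Efficacy Technician for a participant does not perform or facilitate a later efficacy assessment of that participant, but may do so for others.
2. State that the ban on dosing staff applies at every visit for any participant they have dosed.
3. Keep a role-by-participant log with the delegation records, so that a breach is visible and recorded as a deviation.
4. Retain the existing exception for medical necessity, emergencies and participant welfare.

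The cost is protocol wording and a rota by participant, using roles the protocol already requires. The downside is less scheduling flexibility at small sites.

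This does not protect the grading investigator. Where a site already has more than one qualified investigator, AE review should go to one who is not grading that participant. Elsewhere, full separation would need extra staff, and the study report should state the exposure as a limitation of the sign-based endpoints.

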6.4. Study Intervention Compliance

During both stages, on visit days, the morning dose of the assigned study intervention will be administered by designated site personnel; all other doses will be administered by the participant.

On visit days, study intervention compliance will be assumed to be 100% when dosing has been recorded in the eCRF.

In-between office visits, study intervention compliance will be closely monitored by counting the number of used and unused vials/bottles dispensed and returned.

Protocol 2012-201-005 Amendment 3

[figure not shown]
The study center will keep an accurate drug disposition record that specifies the amount of study intervention administered to each participant and the date of administration.

6.5. Concomitant Therapy

Any medication or vaccine (including OTC, prescription medicines, vitamins, herbal supplements, and/or cannabis or other specific categories of interest) that the participant is receiving at the time of enrollment or receives during the study must be recorded along with:

- Indication
- Dates of administration including start and end dates
- Dosage information including dose and frequency

From Screening to the end of the study, site staff will question each participant specifically on the use of concomitant medications. Site staff must notify the sponsor immediately if a participant consumes or applies any concomitant medications that are not permitted by the protocol.

6.5.1. Prohibited Interventions and Washout Before the Study

Participants must discontinue the use of any of the medications or interventions listed in Table 6-2 or Table 6-3 in both eyes for the specified period prior to the Screening visit.

Table 6-2 Stage 1: Required Washout Intervals for Prohibited Medications or Interventions Prior to the Screening Visit

Drug Class/Treatment	Washout Required Prior to the Screening Visit
Artificial tears	24 hours
Systemic immunomodulators (eg, hydroxychloroquine, methotrexate, cyclosporine)	14 days
Corticosteroids administered through any route	7 days
Topical ophthalmic cyclosporine	7 days
Lifitegrast ophthalmic solution (Xiidra)	7 days
TrueTear	7 days
Topical ocular glaucoma medications or topical ocular allergy medications (OTC, herbal, prescription, or nutritional supplements including all mast cell stabilizers and antihistamines)	7 days
Medications associated with the treatment of severe DED and/or Meibomian gland disease such as oral antimuscarinics, cevimeline, oral macrolides, tetracyclines, tetracycline derivatives, and retinoids	14 days
Contact lenses	14 days
Punctal or intracanalicular plugs	1 year
Lid-heating therapy, Meibomian gland probing, or therapeutic Meibomian gland expression	3 months
Systemic medication (including OTC, herbal, prescription, or nutritional supplements) which may affect DED or vision, including but not limited to: antihistamines, cholinergic agents, anticholinergics, beta blocking agents, tricyclic antidepressants and phenothiazines	7 days if the medication was stopped or dosage changed ^a
Hormone replacement therapy program, oral or transdermal contraception, other estrogen, or progesterone treatments, or other medications required for long-term treatment of chronic diseases	7 days if the medication was stopped or dosage changed ^a
Any androgen therapy	7 days if the medication was stopped or dosage changed ^a
Inhalable or ingestible cannabis products or transdermal patches containing THC	30 days

The use of these medications is allowed during Stage 1 of the study provided that the dosing regimen is stable for at least 7 days prior to the Screening visit and does not change at any time during the study.

[figure not shown]
Table 6-3 Stage 2: Required Washout Intervals for Prohibited Medications or Interventions Prior to the Screening Visit

Drug Class/Treatment	Washout Required Prior to the Screening Visit
Artificial tears	24 hours
Systemic immunomodulators (eg, hydroxychloroquine, methotrexate, cyclosporine)	3 months
Corticosteroids administered through any route	3 months
Cyclosporine administered through any route	3 months
Lifitegrast ophthalmic solution (Xiidra)	3 months
TrueTear	14 days
Topical ocular glaucoma medications or topical ocular allergy medications (OTC, herbal, prescription, or nutritional supplements including all mast cell stabilizers and antihistamines)	30 days
Medications associated with the treatment of severe DED and/or Meibomian gland disease such as oral antimuscarinics, cevimeline, oral macrolides, tetracyclines, tetracycline derivatives, and retinoids	3 months
Contact lenses	14 days
Punctal or intracanalicular plugs	1 year
Lid-heating therapy, Meibomian gland probing, or therapeutic Meibomian gland expression	6 months
Systemic medication (including OTC, herbal, prescription, or nutritional supplements) which may affect DED or vision, including but not limited to: antihistamines, cholinergic agents, anticholinergics, beta blocking agents, tricyclic antidepressants and phenothiazines	3 months if the medication was stopped or dosage changed ^a
Hormone replacement therapy program, oral or transdermal contraception, other estrogen, or progesterone treatments, or other medications required for long-term treatment of chronic diseases	3 months if the medication was stopped or dosage changed ^a
Any androgen therapy	3 months if the medication was stopped or dosage changed ^a
Inhalable or ingestible cannabis products or transdermal patches containing THC	30 days

The use of these medications is allowed during Stage 2 of the study provided that the dosing regimen is stable for at least 3 months prior to the Screening visit and does not change at any time during the study.

6.5.2. Permitted Interventions

Therapy considered necessary for the participant's welfare may be given at the discretion of the investigator. If the permissibility of a specific medication/intervention is in question, please contact the sponsor.

The sponsor or designee must be contacted if there are any questions regarding concomitant or prior therapy.

Use of the following systemic medications and vitamins is permitted during the study:

Stage 1:

- Systemic medications (including OTC, herbal, prescription, or nutritional supplements), which may affect DED or vision, including but not limited to the following: antihistamines, cholinergic agents, anticholinergics, antimuscarinics, beta blocking agents, tricyclic antidepressants, and phenothiazines (provided that the dosing regimen is stable for at least 7 days and does not change at any time during the study)
- Hormone replacement therapy program, oral or transdermal contraception, other estrogen
 or progesterone treatments, androgen therapy or other medications required for long-term
 treatment of chronic diseases other than those listed in Section 6.5.4 (provided that the
 dosing regimen is stable for at least 7 days and does not change at any time during the
 study)
- Androgen therapy (provided that the dosing regimen is stable for at least 7 days and does not change at any time during the study)

Stage 2:

- Systemic medications (including OTC, herbal, prescription, or nutritional supplements),
 which may affect DED or vision, including but not limited to the following:
 antihistamines, cholinergic agents, anticholinergics, beta blocking agents, tricyclic
 antidepressants and phenothiazines (provided that the dosing regimen is stable for at least
 3 months and does not change at any time during the study)
- Hormone replacement therapy program, oral or transdermal contraception, other estrogen
 or progesterone treatments, or other medications required for long-term treatment of
 chronic diseases other than those listed in Section 6.5.4 (provided that the dosing regimen
 is stable for at least 3 months and does not change at any time during the study)
- Androgen therapy (provided that the dosing regimen is stable for at least 3 months and does not change at any time during the study)

Any medication taken during the study between the date of the first dose of study intervention and the date of the Exit visit or Early Termination visit will be recorded in the eCRF as a concomitant medication; any medication started after the Exit visit or Early Termination visit will not be considered a concomitant medication and must not be captured in the eCRF.

